7.5 Assignment of Dates of Disease Progression or Disease Response

For all analyses of endpoints as assessed by BICR or by application of mRECIST for HCC to investigator assessed tumor measurements, there may be cases in which disease assessments span a series of dates. For establishing the start date of a subsequently confirmed response in which the disease assessment spans multiple days, the response date assigned will be the latest date of evaluations corresponding to the disease assessment. The date of latest assessment will also be assigned for a mid-study assessment showing SD as the date assigned to that SD for the purposes of censoring duration of SD.

The date of PD will be the 1st date at which any objective diagnostic test provides data indicating PD. Specifically, the date of PD will be the earliest of the following 3 dates:

- Date of PD as indicated by target lesions: if PD is triggered by a change in SLD of target lesions, and all evaluations occurred on the same day, assign that date. If the dates of evaluation of the target lesions vary for the same assessment, assign the first evaluation date among target lesions.
- Date of PD as indicated by non-target lesions: the 1st date for which any non-target lesion exhibits a response of PD.
- Date of PD as indicated by new lesions: the 1st date for which any new lesion is detected.

7.6 Other Efficacy Analyses

7.6.1 Exploratory Alpha Fetoprotein Analysis

Alpha fetoprotein (AFP) assessments will be performed in conjunction with radiologic disease assessments.

A positive AFP outcome will be defined for this exploratory analysis as at least a 20% decrease in AFP serum levels from baseline. Additional definitions of positive AFP outcomes may be explored further. Estimates of positive AFP outcome rate may be reported with 95% confidence intervals and an estimate of the difference in positive AFP outcome rates between groups may be reported and tested for significance with a Pearson chi-square test (or Fisher's exact test, as appropriate). Subjects included in this analysis are those with AFP levels elevated to ≥ 400 $\mu\text{g/L}$ at baseline. Additional criteria may be explored further.

AFP serum levels may be summarized by study visit and may include descriptive statistics such as mean, median, standard deviation, minimum, and maximum, and the changes from baseline. Additional analyses may be performed.

7.6.2 Time to Disease Assessments Analysis

Estimates of median time to disease assessments in each arm using Kaplan Meier methods, reported with 95% confidence intervals will be provided for the first four disease assessments on study along with associated logrank testing. Subjects lost to follow-up or that reach the survival endpoint will be censored at the date of their last disease assessment. For disease assessments that span multiple days, the disease assessment date assigned will be the date when the first imaging scan from the disease assessment was performed.

8 Safety Analysis

8.1 Definition of Safety Variables

The safety parameters assessed are given by the following:

- Frequency, and severity of AEs:
 - All AEs will be classified by System Organ Class (SOC) and Preferred Term (PT) under the Medical Dictionary for Regulatory Activities (MedDRA) system of classification with a severity assigned according to the National Cancer Institute Common Terminology Criteria for Adverse Events (NCI-CTCAE) (Version 4.0), or the rules specified in Section 8.6 of the protocol.
 - Laboratory parameters as presented in Appendix 7 of the protocol.
 - Laboratory toxicities will be graded based on the NCI-CTCAE (Version 4.0).
- Vital signs.
- Anti-mapatumumab antibody response.

All analyses performed on safety will be performed on the as-treated population.

8.2 Analysis of Adverse Events

The safety analysis will consist of a presentation of rates of AEs observed. Specific AEs will be counted once for each subject for calculating rates, but will be presented in total in subject listings. In addition, if the same AE occurs multiple times within a particular subject, the highest severity and level of causality observed will be reported. If any associations of interest between AEs and baseline characteristics are observed, additional stratified results may be presented. All treatment-emergent AEs will be summarized overall, as well as categorized by the MedDRA system of classification. AEs will be presented overall, by severity, by relation to mapatumumab/placebo, and by relation to sorafenib.

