8.2 Reporting Adverse Events to the Sponsor or Designee

The investigator and their designees are responsible for detecting, documenting and reporting events that meet the definition of an AE or SAE.

AM03
15Jul15

Any SAEs assessed as related to study participation (e.g., protocol-mandated procedures, invasive tests, or change in existing therapy) or related to a Human Genome Science product will be recorded from the time a subject consents to participate in the study up to and including any follow-up contact.

Investigators are not obligated to actively seek AEs or SAEs in former study subjects. However, if the investigator learns of any SAE, including a death, at any time after a subject has been discharged from the study, and he/she considers the event reasonably related to the study treatment or study participation, the investigator must promptly notify GSK CMG.

All adverse events (AEs) that are identified from the start of any study agent administration through the specified study follow-up period (through 30 days following administration of the final study agent dose) will be recorded on the paper/electronic Adverse Event Case Report Form (AE case report form). All data fields on the AE case report form will be completed.

Serious Adverse Events (SAEs) must ALSO be recorded on the SAE Worksheet and emailed to GSK CMG at **PPD** (fax backup: **PPD**) within 24 hours of site personnel becoming aware of a SAE, regardless of expectedness. All pages of the SAE Worksheet will be completed, but the SAE worksheet will not be held until all information is available. Additional information and corrections will be provided on subsequent SAE Worksheets as described in the Study Procedure Manual.

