The study is estimated to occur over approximately 24 months. Subjects will continue to receive sorafenib and/or mapatumumab/placebo until radiologic disease progression or unacceptable toxicity. Subjects may discontinue either sorafenib or mapatumumab/placebo separately and remain on treatment. After discontinuation of treatment, subjects will continue to be followed for radiologic disease assessments every 6 weeks (\pm 3 days), starting 6 weeks after the previous disease assessment while on treatment, until documented radiologic disease progression (if not previously documented). Thereafter, subjects will be followed every 3 months for survival until at least 90% of subjects have met the survival endpoint.

If disease progression is based only on a new lesion(s) or is equivocal, images will be provided to the BICR for confirmation of radiologic disease progression prior to discontinuing study treatment. Decisions regarding subject treatment will remain the responsibility of the investigator. Additionally, all images obtained on study will be provided to the BICR for the independent efficacy read.

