5.1 Determination of Sample Size

A total of approximately 100 subjects will be randomly assigned to 1 of 2 arms and treated with either sorafenib + placebo or the 2-agent combination of sorafenib + mapatumumab 30 mg/kg in a 1:1 ratio. A sample size of 50 subjects randomized and treated in each group is sufficient to estimate the median time to progression (TTP) with a precision of approximately -1.9 months to +2.6 months relative to the observed median. In addition, a sample size of 50 patients per arm will provide 80% power to detect an improvement in TTP from 5.5 to 8.9 months with at a one-sided significance level of 0.10.

6 Study Subjects

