Dose reductions are not permitted for mapatumumab/placebo. However, any mapatumumab/placebo dosing interruptions that take place resulting in a reduction from the intended dose will be considered dose reductions. Sorafenib dose reductions will be summarized. A dose reduction will be defined as a physician decision to reduce the prescribed dose to a lower level relative to the previous prescribed dose while on treatment (including reductions to 0 mg which would constitute dose omission, also analyzed separately, see below). The number of subjects requiring at least 1 dose reduction will be summarized along with the maximum dose level reduction attained for each subject. In addition, rates of subjects requiring dose reductions due to adverse events (AEs) or laboratory abnormalities will be provided. Statistical analysis of dose reduction rates will include Pearson chi-square testing (or Fisher's exact testing, as appropriate) for differences between groups. Dosing errors for either mapatumumab/placebo or sorafenib will not be identified as dose reductions in the analysis.

In addition, all sorafenib dose reductions observed (possibly multiple events per subject) will be summarized by treatment group and reason. The percent of dose reductions that resulted in an eventual return to the original dose level from which the subject was reduced will be calculated.

The number of subjects requiring sorafenib dose omissions will be summarized by treatment group. A subject will be determined to have a dose omission if the prescribed dose for a given time interval (while on sorafenib treatment) is 0 tablets per day. Statistical analysis of the rate of subjects requiring dose omission (overall, due to AEs,

and due to laboratory abnormalities) will include Pearson chi-square testing (or Fisher's exact testing, as appropriate). In addition, all dose omissions (possibly multiple events per subject) will be summarized by treatment group and reason.

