8.5 Clinical Laboratory Evaluation

Laboratory parameters will be assessed at baseline and throughout the study. Frequencies of worst observed grade 0 to 4 toxicity as defined by the NCI-CTCAE (Version 4.0) will be presented for each laboratory parameter.

Also, laboratory parameters will be assessed by presenting tables containing information related to 2-grade (or greater) laboratory shifts from baseline. Specific laboratory tests are listed in Appendix 7 of the protocol. Some laboratory tests can be graded for toxicity for either an increase or a decrease (sodium, potassium, magnesium, calcium, and glucose). Because of this, they will be listed twice in each presentation, once to detect an increase and once to detect a decrease (eg, hypoglycemia and hyperglycemia). For presentation of shifts from baseline in these cases, a 0 at baseline will indicate an absence of toxicity in the direction being detected (eg, for shift tables for hyperglycemia, a 0 at baseline will indicate an absence of hyperglycemia). For laboratory tests not graded by the NCI-CTCAE, tables summarizing shifts outside of the normal range will be presented.

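### If mapatumumab delays progression, ever-affected proportions for adverse events, worst laboratory grades and sorafenib reductions or omissions are biased against it for events whose risk persists through treatment

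*SAP*

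**What the plan says.** SAP 4 (Study Design) sets no fixed treatment length: "Subjects will continue to receive sorafenib and/or mapatumumab/placebo until radiologic disease progression or unacceptable toxicity". Protocol 8.2 collects adverse events from first dose "through 30 days following administration of the final study agent dose", so the collection window lengthens with treatment. SAP 5.1 sizes the trial for "80% power to detect an improvement in TTP from 5.5 to 8.9 months", with 50 subjects per arm.

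The safety comparisons are then as follows.

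- **Adverse events (SAP 8.2):** "The safety analysis will consist of a presentation of rates of AEs observed", and "Specific AEs will be counted once for each subject for calculating rates". No between-arm test is planned.
- **Laboratory results (SAP 8.5):** "Frequencies of worst observed grade 0 to 4 toxicity", plus shifts of two or more grades from baseline. These are also descriptive.
- **Sorafenib dose reductions and omissions (SAP 6.2):** "The number of subjects requiring at least 1 dose reduction will be summarized", and "Statistical analysis of dose reduction rates will include Pearson chi-square testing", or Fisher's test where appropriate. Omissions are handled the same way. No significance level is given for these tests.

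SAP 6.2 also reports duration of exposure, dose intensity and relative dose intensity by arm. No section gives a time-to-first-event, person-time or fixed-window safety comparison, and SAP 10 adds nothing further.

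**The concern.** A subject who progresses later is treated longer, has more blood draws, and has more time in which to record a first event. If mapatumumab delays progression, its arm accumulates more ever-affected subjects even when the risk per month is the same. The crude comparison then mixes toxicity with length of observation, in the direction that penalises an effective drug.

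Safety of the combination is the first secondary objective. The confusion arises in the one scenario the trial is built to detect, a positive TTP result, which is also where a clear reading of safety matters most for further development. For sorafenib reductions and omissions there is the added problem of a formal test whose null hypothesis, equal proportions ever affected, is false when monthly risks are equal but exposure is not.

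**Working it through.** **The plan's own figure.** With hazard ratio 5.5/8.9 = 0.618, one-sided level 0.10 and 80% power, the Schoenfeld formula gives 4(1.2816 + 0.8416)²/(ln 0.618)² = 77.8, so 78 events. That is attainable from 100 subjects, so the stated 80% reproduces and the medians can be used as the design effect.

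**Inputs.** From the documents: medians 5.5 and 8.9 months, 50 per arm, 1:1 allocation, 30-day tail for adverse events. Assumed: exponential time to progression, treatment stopping at progression, one constant first-event hazard λ in both arms, and a two-sided 5% test.

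**Time at risk.** Mean treatment time is median/ln 2: 7.9 against 12.8 months, ratio 1.62. With the 30-day tail (0.99 month) it is 8.9 against 13.8, ratio 1.55.

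**Dose reductions (no tail).** With μ = ln 2/median, the probability of ever being affected is λ/(λ + μ). Here μ is 0.1260 for control and 0.0779 for mapatumumab. A 30% control proportion gives λ = 0.30 × 0.1260/0.70 = 0.0540. For mapatumumab, 0.0540/(0.0540 + 0.0779) = 41.0%.

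**Adverse events (tail f = 0.99 month).** The probability is 1 − exp(−λf) × μ/(λ + μ). A 30% control proportion gives λ = 0.0460, and 39.9% for mapatumumab. Control values of 10%, 20% and 50% become 14.7%, 27.9% and 60.8%.

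**Rejection by the SAP 6.2 test.** Exact binomial enumeration of the Pearson test, 50 per arm. With equal proportions it rejects in about 5% of trials. The last two columns add a discontinuation hazard of 0.05 or 0.10 per month to μ in both arms. Those rates are assumptions, as the documents give none.

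| Control proportion | Mapatumumab, equal hazard | Rejection | Rejection, 5%/month other stops | Rejection, 10%/month other stops |
|---|---|---|---|---|
| 20% | 28.8% | 17.7% | 10.3% | 8.0% |
| 30% | 41.0% | 20.7% | 11.5% | 8.5% |
| 40% | 51.9% | 23.8% | 13.3% | 9.8% |

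Without other stops, almost all rejections are against mapatumumab.

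**Sensitivity for a 30% adverse event (with tail).** Other discontinuation at 5% or 10% per month gives 36.2% or 34.4%. A mapatumumab median TTP of 6.5 or 7.5 months gives 33.3% or 36.2%. Equal medians give 30%, so no bias.

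**Early-onset events.** If the hazard acts only in the first 42 days (w = 1.38 months), the on-treatment probability is λ/(λ + μ) × [1 − exp(−(λ + μ)w)]. A 30% control proportion (λ = 0.285) becomes 30.9%, with 5.1% rejection. With the 30-day tail the simulated crude figures are 30% and 30%.

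**Does an exposure-adjusted rate solve it?** Under a constant equal hazard it does: in simulation, 4.6 against 4.6 first events per 100 subject-months, with 4.9% rejection. Under an equal hazard confined to 42 days it does not. The rate ratio is 0.65, because later event-free time dilutes the longer-treated arm. If the early hazard is truly 1.5 times higher on mapatumumab, the crude proportions show the excess (30% against 41%), but the rate ratio is only 1.07.

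**The case against.** The strongest case against has four parts.

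1. **The effect is conditional.** It needs a TTP benefit and a risk that lasts through treatment, and the documents give no data on event timing. A reader might infer that the planned tables would show excess toxicity where none exists. The documents do not support that as a general statement. For early-onset events the distortion is about 1 point or less. This stands, and it bounds the concern.

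2. **Exposure is not ignored.** A reader might infer that every between-arm safety summary disregards it. SAP 6.2 reports duration, dose intensity and relative dose intensity by arm, and vital signs are summarised by visit, so that inference is too broad. But these quantities never enter the adverse-event, laboratory or reduction comparisons, and an average dose intensity does not give the monthly risk of a first reduction.

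3. **Adverse events and laboratory grades are not tested.** This is correct. Inflated rejection applies only to the SAP 6.2 tests, and the 5% level is an assumption because the SAP states none.

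4. **Sorafenib time is not TTP.** Subjects also stop for toxicity, illness or withdrawal, and sorafenib can stop alone. This stands and roughly halves the inflation or more, as the table shows. It does not remove it at the assumed rates.

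A further tempting inference is that exposure-adjusted rates are the remedy. The early-onset calculation shows that, used alone, they could conceal real toxicity.

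**Conclusion.** The concern holds, conditionally. If mapatumumab delays progression, ever-affected proportions are biased against it for events whose risk continues through treatment, and the plan contains no comparison that removes this.

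At the design effect with an equal constant hazard and progression as the only reason to stop, the spurious excess at 30% control incidence is about 10 points for adverse events and 11 for dose reductions. The SAP 6.2 test then rejects in about 18% to 24% of trials at control rates of 20% to 40%, or about 8% to 13% with the assumed other discontinuation. For events limited to the first two cycles the excess is about 1 point or less. With no TTP benefit it is zero.

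The direction follows from the plan's own rules. The size rests on event timing and stopping rates that the documents do not give. The primary efficacy analysis is unaffected.

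**What to change.** **SAP 6.2.** Replace the chi-square/Fisher comparison of sorafenib reductions and omissions with time to first reduction and time to first omission: Kaplan-Meier curves (or their complement, shown as cumulative incidence) with a log-rank test, censored at end of sorafenib. State the test level, and whether a permanent stop of sorafenib for toxicity counts as an event. The counts of subjects ever affected can stay as description.

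**SAP 8.2, 8.3 and 8.5.** Keep the crude percentages. For key categories (any adverse event, Grade 3 or higher, SAEs, Grade 3/4 laboratory toxicities, common preferred terms) add by arm:

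- time-to-first-event summaries, with time at risk ending at the first event or 30 days after the last dose;
- a table for a fixed early window, with its length fixed before unblinding.

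Exposure-adjusted rates may be shown beside these, but not alone.

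**Cost.** SAP wording and some additional tables. The plan already relies on dosing, event and laboratory dates, SAP 6.2 already derives exposure, and SAP 7.6.2 already uses Kaplan-Meier and log-rank methods for assessment timing. No new data and no change to trial conduct are needed.

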8.3 Serious Adverse Events

Serious adverse events (SAEs) will be summarized by relation to mapatumumab/placebo and by relation to sorafenib.

8.4 Deaths and Discontinuations due to Adverse Events

A summary of all subjects who die due to any cause or who discontinue study agent (mapatumumab/placebo and/or sorafenib) due to AEs will be provided.

8.5 Clinical Laboratory Evaluation

Laboratory parameters will be assessed at baseline and throughout the study. Frequencies of worst observed grade 0 to 4 toxicity as defined by the NCI-CTCAE (Version 4.0) will be presented for each laboratory parameter.

Also, laboratory parameters will be assessed by presenting tables containing information related to 2-grade (or greater) laboratory shifts from baseline. Specific laboratory tests are listed in Appendix 7 of the protocol. Some laboratory tests can be graded for toxicity for either an increase or a decrease (sodium, potassium, magnesium, calcium, and glucose). Because of this, they will be listed twice in each presentation, once to detect an increase and once to detect a decrease (eg, hypoglycemia and hyperglycemia). For presentation of shifts from baseline in these cases, a 0 at baseline will indicate an absence of toxicity in the direction being detected (eg, for shift tables for hyperglycemia, a 0 at baseline will indicate an absence of hyperglycemia). For laboratory tests not graded by the NCI-CTCAE, tables summarizing shifts outside of the normal range will be presented.

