4.1 Inclusion Criteria

Subjects enrolled in the study must meet the following inclusion criteria:

1. Child-Pugh Class A (see [Appendix 1](#)).
2. Barcelona Clinic Liver Cancer (BCLC) advanced stage (C) hepatocellular carcinoma, or BCLC intermediate stage (B) hepatocellular carcinoma if treatment with transarterial chemoembolization is not considered appropriate (see [Appendix 2](#)).
3. Measurable disease demonstrating intratumoral arterial enhancement by contrast enhanced computerized tomography (CT), with use of multislice scanners, or contrast enhanced dynamic magnetic resonance imaging (MRI), with at least 1 tumor lesion that meets the following criteria:
 - Located in the liver.
 - Can be accurately measured in at least 1 dimension.
 - Well delineated area of viable, hypervascular (contrast enhancement in the arterial phase) tumor that is > 2 cm in the axial plane.
 - Suitable for repeat measurement.
 - Not previously treated with locoregional or systemic treatment unless the lesion shows a well-delineated area of viable (contrast enhancement in the arterial phase) tumor that is > 2 cm in the axial plane. (If the lesion is poorly demarcated or exhibits atypical enhancement as a result of the previous intervention, then it cannot be selected as a target lesion).
4. Radiologic eligibility (measurable disease) must be confirmed by the BICR prior to randomization.
5. Adequate bone marrow, renal and liver function:
 - Absolute neutrophil count $\geq 1.5 \times 10^9 / \text{L}$ or $\geq 1500 / \text{mm}^3$.
 - Platelet count $\geq 50 \times 10^9 / \text{L}$ or $\geq 50,000 / \text{mm}^3$.
 - Hemoglobin $\geq 9 \text{ g/dL}$ ($\geq 5.6 \text{ mmol/L}$) without growth factor support or transfusional support.
 - Serum creatinine level $\leq 2.0 \text{ mg/dL}$ or $\leq 176.8 \mu\text{mol/L}$.
 - Total bilirubin $< 3.0 \text{ mg/dL}$ or $< 51.3 \mu\text{mol/L}$.
 - Aspartate transaminase (AST) and alanine transaminase (ALT) $\leq 5.0 \times$ upper limit of normal.
 - Amylase and lipase $\leq 1.5 \times$ upper limit of normal.
 - Serum albumin $\geq 2.8 \text{ g/dL}$ or $\geq 28 \text{ g/L}$.
 - International normalized ratio ≤ 1.5 .
6. Performance status of 0, 1 or 2 on the Eastern Cooperative Oncology Group (ECOG) Scale (see [Appendix 3](#)).
7. Age 18 years or older.

AM01
21Dec10

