5.1.4 Mapatumumab/Placebo Dose Toxicity/Delay

Mapatumumab/placebo will be discontinued for Grade 4 transaminase elevations of any duration if they are considered related to mapatumumab.

AM01
21Dec10

Mapatumumab/placebo may be delayed up to 2 weeks for toxicities considered related to mapatumumab as described below or if the investigator believes that a delay in dosing is warranted in the interest of subject safety.

The National Cancer Institute Common Terminology Criteria for Adverse Events (NCI-CTCAE, Version 4.0) will be used to grade AEs.

- Grade 4 neutropenia for > 7 consecutive days or febrile neutropenia.
- Grade 4 thrombocytopenia.
- Grade 3 or greater non-hematologic AEs except transient transaminase, amylase and lipase abnormalities for which the following criteria will apply:
 - Grade 3 or Grade 4 elevations in transaminases that do not resolve to baseline or Grade 1 before the next cycle.
 - Grade 3 elevations in lipase or amylase associated with clinical/imaging findings of pancreatitis, or resulting in chronic damage to the pancreas.
 - Any Grade 4 elevations in lipase or amylase for > 4 consecutive days.

If mapatumumab/placebo is delayed for toxicity and the toxicity does not resolve (\leq Grade 1) or return to baseline within 2 weeks after the delayed dose was originally scheduled (based on a 21-day treatment cycle), the subject will be withdrawn from further treatment with mapatumumab/placebo. If mapatumumab/placebo is delayed because the investigator believes a delay is warranted in the interest of subject safety and dosing of mapatumumab/placebo is not resumed within 2 weeks after the delayed dose was originally scheduled (based on a 21-day treatment cycle), the subject will be withdrawn from future treatment with mapatumumab/placebo. Sorafenib dosing will continue while mapatumumab/placebo dosing is held. The subject will continue receiving sorafenib until radiologic progressive disease or an unacceptable toxicity occurs, at the discretion of the Investigator.

Doses of mapatumumab may not be altered.

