7.4 Exploratory Assessments (B and T Lymphocyte Subsets)

7.4.1 Rationale for B and T Lymphocyte Analysis

Over 400 subjects have received mapatumumab in doses ranging from 0.01 to 30 mg/kg across multiple Phase 1 and Phase 2 clinical trials in subjects with solid and hematologic malignancies. While there is no evidence to date that mapatumumab exacerbates adverse events associated with chemotherapy, the most commonly observed laboratory abnormality associated with mapatumumab has been lymphopenia. The lymphopenia has been intermittent and reversible and was not associated with infectious events. However, the lymphocyte subpopulation(s) affected have not been characterized.

The evaluation of lymphocytes will include complete blood count/differential and lymphocyte subpopulation analysis (numbers and percentages of T and B cells) by flow cytometry at a central laboratory. Blood samples will be examined by flow cytometry for levels of T helper (CD4+), T cytotoxic (CD8+) and mature B cells (CD19+).

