9.4 Safety

9.4.1 Definition of Safety Variables

The safety parameters assessed are given by the following:

- Frequency, and severity of adverse events (AEs):
 - All AEs will be classified by System Organ Class and Preferred Term under the Medical Dictionary for Regulatory Activities (MedDRA) system of classification with a severity assigned according to the NCI-CTCAE (Version 4.0, 29 May 2009), or the rules specified in Section 8.6.
 - Laboratory parameters as presented in [Appendix 7](#).
 - Laboratory toxicities will be graded based on the NCI-CTCAE (Version 4.0, 29 May 2009).
- Anti-mapatumumab antibody response.
- Vital signs.
- For frequency and severity of adverse events and laboratory toxicity grading, counts and rates will be presented.

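### For laboratory tests with no entry limit, chiefly lymphocytes, the tables in SAP 8.5 cannot separate new or worsened Grade 3/4 from Grade 3/4 already present at entry

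*SAP*

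**What the plan says.** SAP 8.5 plans two displays for laboratory tests that carry an NCI-CTCAE grade. The first is a frequency table: "Frequencies of worst observed grade 0 to 4 toxicity as defined by the NCI-CTCAE (Version 4.0) will be presented for each laboratory parameter". The second is the shift display: "laboratory parameters will be assessed by presenting tables containing information related to 2-grade (or greater) laboratory shifts from baseline". Ungraded tests are handled separately: "For laboratory tests not graded by the NCI-CTCAE, tables summarizing shifts outside of the normal range will be presented". The two-grade rule therefore does not apply to them.

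Protocol 9.4.1 asks for no more than this: "For frequency and severity of adverse events and laboratory toxicity grading, counts and rates will be presented". Neither document plans a table of baseline grade by worst grade, or a display of one-grade shifts. SAP 5 takes the Cycle 1/Day 1 predose value as the usual baseline, with the closest screening value as substitute.

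On the background, Protocol 7.4.1 states that "the most commonly observed laboratory abnormality associated with mapatumumab has been lymphopenia". Protocol 4.1, criterion 5, sets entry limits for AST and ALT (up to 5.0 times the upper limit of normal), total bilirubin and several other tests. It sets none for lymphocytes or GGT, although Protocol Appendix 7 lists both for collection.

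**The concern.** A two-grade threshold treats a move from Grade 0 to 2 as reportable and a move from Grade 2 to 3 as not. Someone who starts at Grade 2 enters the shift table only on reaching Grade 4, and someone who starts at Grade 3 can never enter it.

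The worst-grade table would make up for this if it described only what happened after dosing, or if it were split by baseline grade. The SAP says neither. For a test on which subjects can enter at Grade 3 or 4, the plan then has no display that answers a basic safety question: how many subjects in each arm developed, or worsened to, Grade 3 or 4 on study?

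Lymphocytes are the test for which that question is most natural. Protocol 1.4.3 reports that randomized Phase 2 data suggest mapatumumab may increase rates of lymphopenia. Protocol 1.6 gives Phase 1b figures for the combination with sorafenib: Grade 3 lymphopenia in 3/16 and Grade 4 in 2/16. It does not say how many of those subjects were already at that grade at entry.

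**Working it through.** The plan states no figure for this point, so there is nothing to reproduce. The check is a count of grade pairs, followed by a comparison of what each table shows.

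**1. Which worsenings the shift rule shows.** On the 0 to 4 scale there are 4 + 3 + 2 + 1 = 10 worsening pairs. The rule shows a pair if worst grade minus baseline grade is at least 2.

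- Shown (6): 0-2, 0-3, 0-4, 1-3, 1-4, 2-4.
- Not shown (4): 0-1, 1-2, 2-3, 3-4.
- Of the 7 pairs that end at Grade 3 or 4, 5 are shown. The two missing are 2-3 and 3-4.

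**2. What the two tables show together for a test with no entry limit.**

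| Course of a subject | Shift table | Worst-grade table |
|---|---|---|
| Grade 0, rising to 2 | shown | Grade 2 |
| Grade 2, rising to 3 | not shown | Grade 3 |
| Grade 3 throughout | not shown | Grade 3 |
| Grade 3 at entry, at most 2 afterwards | not shown | Grade 3 if the baseline sample counts, otherwise Grade 2 |
| Grade 3, rising to 4 | not shown | Grade 4 |
| Grade 4 throughout | not shown | Grade 4 |

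The second and third rows look identical in both displays, as do the last two.

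**3. Can the answer be recovered by subtraction?** Let n(b,w) be the number of subjects with baseline grade b and worst grade w, baseline sample included. Assume the layout most favourable to the plan, in which the shift table lists each pair separately.

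- Grade 3 total minus shown pairs: [n(0,3) + n(1,3) + n(2,3) + n(3,3)] − [n(0,3) + n(1,3)] = n(2,3) + n(3,3).
- Grade 4 total minus shown pairs: n(3,4) + n(4,4).

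Each remainder mixes on-study worsening with a grade present at entry. If worst grade is read as post-baseline only, subjects who improve from 4 to 3 join the first remainder, and it still cannot be separated.

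**4. The same subtraction for a capped test.** Take AST or ALT, limited to 5.0 times the upper limit of normal. Assume that Grade 3 starts above that value in NCI-CTCAE version 4.0; the documents do not reproduce the cut-points. Then no subject is at Grade 3 or 4 at screening, so n(3,3), n(3,4) and n(4,4) are zero apart from drift before Cycle 1/Day 1. Protocol 6.1 allows screening tests up to 28 days before enrollment. The first remainder becomes n(2,3), so the information is largely there.

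**5. Illustrative size.** The documents give no distribution of baseline grades. With 50 subjects per arm, a share q starting at Grade 2 on a given test, and a share r of those rising to Grade 3, the number missing from that test's shift table is 50 × q × r.

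- Low: 50 × 0.05 × 0.10 = 0.25 per arm.
- Middle: 50 × 0.10 × 0.25 = 1.25 per arm.
- High: 50 × 0.30 × 0.50 = 7.5 per arm.

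Both shares are assumptions.

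**The case against.** The strongest reply is that nothing is lost. The shift table is an addition to the worst-grade table, and every Grade 3 or 4 value is counted in the latter. The trial is randomized 1:1 with a placebo control, so grades at entry are balanced in expectation and the comparison of arms remains interpretable. No test, endpoint or stopping decision uses these tables. All of this stands, and it is why the point is minor. It does not remove the point: with about 50 subjects per arm and stratification only by BCLC stage and ECOG status, entry grades can differ by chance, and Grade 3 already present dilutes any contrast.

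A second reply is that adverse event reporting fills the gap. It does so in part. Under Protocol 8.3 a laboratory change tied to an intervention must be reported, and SAP 8.2 tabulates adverse events by severity. Without an intervention or clinical sequelae, reporting is discretionary. The footnote to Protocol Table 5-4 lets subjects with Grade 3 or 4 lymphopenia stay on sorafenib uninterrupted at the investigator's discretion. Lymphopenia is not among the listed mapatumumab delay criteria in 5.1.4 or the Protocol Specified Events in 8.4. It can therefore reach Grade 3 or 4 without a mandatory report.

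A third reply is that SAP 8.5.1 tabulates B and T lymphocyte subsets. Those samples are limited to Cycles 1 and 2, and no graded comparison with baseline is described.

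A reader might infer more than the documents support, in particular about the liver. Subjects may be admitted with abnormal liver tests, but none are required to be, and step 4 of the working shows that the AST/ALT cap makes this where the two tables together work best. Nor does the protocol single out hepatic tests as an effect of mapatumumab. Section 1.4.3 describes Grade 3 or 4 hepatic abnormalities with single-agent use as relatively uncommon, with no significant trend, and 1.4.2 says clinical results showed no evidence of hepatotoxicity. Section 1.6 reports Grade 3 bilirubin in 4/16 and Grade 4 in 1/16 but does not attribute them to mapatumumab. It is also tempting to say that a transaminase shift from Grade 2 becomes visible only at the stopping point. The rule is conditional, however: "Mapatumumab/placebo will be discontinued for Grade 4 transaminase elevations of any duration if they are considered related to mapatumumab".

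**Conclusion.** The point holds as a limited gap in presentation. The two-grade rule omits 2-to-3 and 3-to-4 worsening for graded tests, and the worst-grade table is neither crossed with baseline nor expressly post-baseline. For tests with no entry limit, the two displays together cannot separate new or worsened Grade 3/4 from Grade 3/4 present at entry. Lymphocytes are the main case. GGT is a second, provided NCI-CTCAE grades it, which the documents do not state.

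The reading that rises to Grade 3 go unreported is not supported: the counts are in the worst-grade table, and only their link to baseline is missing. For tests capped at entry the loss is small, subject to the assumed version 4.0 cut-points and to drift between screening and Cycle 1/Day 1. The number of subjects affected is unknown, and the 0.25 to 7.5 per arm rests on assumed shares. No efficacy conclusion is touched. This is a minor improvement to a safety display.

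**What to change.** In SAP 8.5, for each NCI-CTCAE-graded parameter and by arm:

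1. Replace the two-grade shift table with a cross-table of baseline grade by worst post-baseline grade. This shows all 10 worsening pairs instead of 6, as well as subjects who do not change. Tests graded in both directions get one table per direction, as the SAP already intends.
2. Define worst grade on post-baseline samples only, using the SAP 5 definition of baseline. On its own this is not enough, because a subject who stays at Grade 3 would still be counted with those who rise to it.
3. Report the number of subjects with Grade 3 or higher that is at least one grade above baseline.

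If the two-grade table must be kept, adding every worsening that ends at Grade 3 or 4 would show 8 of the 10 pairs and all 7 that end at those grades.

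The cost is a revised table shell and a sentence or two in the SAP. All the data are already collected.
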